7.5.2 Prohibited Medication/Therapy and Procedures During the Trial

The following medications and procedures are not allowed from C1/D1, or as specified in the inclusion/exclusion criteria, until the EOT Visit:

• Anti-cancer treatment, including cytotoxic or cytostatic agents, hormonal therapy (except as physiologic hormone replacement) and EGFR/HER-targeting therapies

Confidential Page 70 of 156

- Radiotherapy against target lesion(s) (Part 2 only)
- Systemic immunosuppressive or systemic hormonal therapy (> 10 mg daily prednisone equivalent) with the exception of the following allowed therapies:
 - o Hormonal therapy (e.g., Megace) for appetite stimulation
 - o Nasal, ophthalmic, inhaled, and topical glucocorticoid preparations
 - o Hormone replacement therapy at standard doses for end-organ failure
 - Steroid therapy as prophylaxis for contrast reactions
 - o Intra-articular steroid injections
 - Hormonal therapy for ovarian suppression, hormonal contraceptive therapy, postmenopausal HRT
 - o GnRH analogs in patients with prostate cancer
 - Low-dose maintenance steroid therapy for other conditions (excluding steroid tapers for brain edema/metastases/radiation)
 - Higher dose steroid therapy for treatment of an acute intercurrent illness in patients with stable disease or an ongoing response. In such situations, study drug treatment should be interrupted for the duration of immunosuppressive therapy
- Prophylactic use of hematopoietic growth factors during Cycle 1
- Use of alcohol- or peroxide-containing mouthwashes
- Major surgery that would preclude the patient from complying with the requirements of the protocol

If any one of the above listed medications/procedures becomes necessary during the trial, the patient must be withdrawn from Pan-HER and the EOT Visit should be performed. The 1M FUP Visit should then be performed, no less than 1 month (30+7 days) after the last dose of Pan-HER.

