8.10 Follow-up Assessments

Assessments at the 1M FUP Visit include disease status and subsequent cancer therapy.

Part 2 ONLY: After the 1M FUP Visit, the Investigator will make every effort to obtain follow-up information on response assessment and/or OS every 2 months. Response assessment follow-up is required in the event of an ongoing SD, PR or CR, as per RECIST v1.1 at the 1M FUP Visit, until PD or another therapeutic intervention is initiated. Survival follow-up is required until death, withdrawal of consent, or termination of the trial. This continued follow-up does not require an in-person visit at the trial site, but may be obtained by collection of data/documentation.

Confidential Page 84 of 156

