3.2 Endpoints and Associated Variables

Refer to the Schedule of Assessments for timing of assessments.

Primary Endpoint - Part 1, Dose-Escalation

The primary objective of the dose-escalation part is to assess the safety and tolerability of Pan-HER. This will be assessed by the primary endpoint for Part 1: **occurrence of DLTs during Cycle 1 for each of the Pan-HER dose regimens.**

Secondary Efficacy Endpoints

- Documented OR, defined as documented PR or CR, from baseline to end of trial participation (in patients with measurable disease only) (as measured in Part 1)
- Best overall response by RECIST v1.1, categorized as Complete Response (CR), Partial Response (PR), Stable Disease (SD), Progressive Disease (PD), and Not Evaluable (NE)
- Disease Control Rate (DCR)
- Changes in sum of diameters of target lesions from baseline to end of trial participation
- Time to documented PD (Time To Progression [TTP])

PAREXEL International
Statistical Analysis Plan Template for Early Phase Studies

Symphogen A/S

Sym013-01

Secondary Safety Endpoints

- Nature, incidence and severity of AEs measured from baseline to end of trial participation
- AEs leading to dose-reductions, dose delays and permanent treatment cessation
- Changes in safety laboratory values from baseline to end of trial participation
- Changes in vital signs and physical examinations from baseline to end of trial participation
- Occurrence of ADA to Pan-HER measured in serum at selected timepoints from baseline to end of trial participation

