3.2.1 Efficacy Variables

3.2.1.1 Tumor Response according to RECIST v1.1

The anti-tumor activity of Pan-HER will be assessed according to RECIST, v 1.1 using CT or MRI. The use of CT or MRI must be consistent per patient throughout the trial.

Disease Status Evaluation by CT or MRI will occur at:

- Screening

Note: A CT/MRI performed within 28 days prior to Day 1 may be used for evaluation of eligibility and as baseline scan, provided that the CT/MRI has been performed according to the CTP requirements

- End of Cycle 2 and end of every second cycle thereafter, i.e. Cycle 4, 6, 8 etc.

Note: End of cycle assessments may be conducted at any time during the week prior to Day 1 of the next cycle

- After Suspected Progressive Disease (PD) (as soon as possible)
- Confirmation of response, to be performed 28 (+7) days after the first assessment of CR/PR

PAREXEL International
Statistical Analysis Plan Template for Early Phase Studies

Symphogen A/S

Sym013-01

- EOT (if >3 weeks since previous CT/MRI)
- At 1M FUP (if PD was not documented before or at EOT)

If PD is documented at any time, no further disease assessments will be required. Patients with documented PD will be discontinued from Pan-HER so that alternative management of their malignancy may be considered.

For all imaging time points, the following will be recorded as per RECIST v1.1: Target lesions including size, location, and type (nodal/non-nodal); sum of diameters of target lesions; any new lesions noted during trial, including size, location, and type (nodal/non-nodal); response assessment at each visit (PD, SD, PR, CR or Not Evaluable [NE]), per investigators evaluation.

Tumor evaluation according to RECIST 1.1 will be the basis for the derivation of all efficacy endpoints. To be assigned a status of confirmed PR or CR, changes in disease status must be confirmed by repeat imaging studies performed no less than 28 days (4 weeks) after the criteria for response are first met. In the case of SD, follow-up measurements must have met the SD criteria at least once after trial entry at a minimal interval in general no less than 6-8 weeks from first dose of Pan-HER; for the scope of derivation of SD as best overall response, a minimal SD duration of 6 week will be required.

The following anti-tumor response endpoints will be derived based on Tumor evaluation according to RECIST 1.1:

- Target and Non Target Response at each timepoint will be derived according to RECIST 1.1 [1].

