CR	CR	No	CR
CR	Non-CR/non-PD	No	PR
CR	Not evaluated	No	PR
PR	Non-PD or not all evaluated	No	PR
SD	Non-PD or not all evaluated	No	SD
Not all evaluated	Non-PD	No	NE
PD	Any	Yes or No	PD
Any	PD	Yes or No	PD
Any	Any	Yes	PD

CR = complete response, PR = partial response, SD = stable disease, PD = progressive disease, and NE = inevaluable.

Table 2 – Time point response: patients with non-target disease only.

Non-target lesions	New lesions	Overall response
CR	No	CR
Non-CR/non-PD	No	Non-CR/non-PD ^a
Not all evaluated	No	NE
Unequivocal PD	Yes or No	PD
Any	Yes	PD

CR = complete response, PD = progressive disease, and NE = inevaluable.
 a 'Non-CR/non-PD' is preferred over 'stable disease' for non-target disease since SD is increasingly used as endpoint for assessment of efficacy in some trials so to assign this category when no lesions can be measured is not advised.

- Confirmed Best Overall Response (BOR) by RECIST v1.1.

Per RECIST 1.1[1]:

'the best overall response is the best response recorded from the start of the study treatment until the end of treatment taking into account any requirement for confirmation.'
'Specifically, in non-randomised trials where response is the primary endpoint, confirmation of PR or CR is needed to deem either one the 'best overall response'.' *'Best response determination in trials where confirmation of complete or partial response is*

PAREXEL International
Statistical Analysis Plan Template for Early Phase Studies

Symphogen A/S
Sym013-01

required: Complete or partial responses may be claimed only if the criteria for each are met at a subsequent time point as specified in the protocol (generally 4 weeks later). In this circumstance, the best overall response can be interpreted as in Table 3.'

Table 3 of above-mentioned paper [1] is reported below and will be used to derive confirmed Best Overall Responses. In this study a minimum SD duration of 6 week will be used as criterium to confirm SD as Best Overall Response.

Table 3 – Best overall response when confirmation of CR and PR required.

Overall response First time point	Overall response Subsequent time point	BEST overall response
CR	CR	CR
CR	PR	SD, PD or PR ^a
CR	SD	SD provided minimum criteria for SD duration met, otherwise, PD
CR	PD	SD provided minimum criteria for SD duration met, otherwise, PD
CR	NE	SD provided minimum criteria for SD duration met, otherwise NE
PR	CR	PR
PR	PR	PR
PR	SD	SD
PR	PD	SD provided minimum criteria for SD duration met, otherwise, PD

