PR	NE	SD provided minimum criteria for SD duration met, otherwise NE
NE	NE	NE

CR = complete response, PR = partial response, SD = stable disease, PD = progressive disease, and NE = inevaluable.

a If a CR is truly met at first time point, then any disease seen at a subsequent time point, even disease meeting PR criteria relative to baseline, makes the disease PD at that point (since disease must have reappeared after CR). Best response would depend on whether minimum duration for SD was met. However, sometimes 'CR' may be claimed when subsequent scans suggest small lesions were likely still present and in fact the patient had PR, not CR at the first time point. Under these circumstances, the original CR should be changed to PR and the best response is PR.

Patients with non-target disease only, may have a time point response of NON-CR/NON-PD, these responses will be included in the count of SD.

Determinations of Best Overall Responses derived as described will be reviewed by Symphogen and PAREXEL on a patient by patient basis across time.

- Unconfirmed BOR by RECIST v1.1:

Per RECIST 1.1 [1]: in cases where confirmation of complete or partial response is not required the Best response is defined as the best response across all time points (for example, a patient who has SD at first assessment, PR at second assessment, and PD on last assessment has a best overall response of PR). When SD is believed to be best unconfirmed response, it must also meet the protocol specified minimum time from baseline.

PAREXEL International
Statistical Analysis Plan Template for Early Phase Studies

Symphegen A/S
Sym013-01

Patients with non-target disease only, may have a time point response of NON-CR/NON-PD, these responses will be included in the count of SD.

- Documented objective response (OR) confirmed and unconfirmed, based on determination of confirmed and unconfirmed best overall response (BOR) per RECIST v1.1.

Confirmed OR is defined as the percentage of patients who had confirmed CR or PR.

Unconfirmed OR is defined as the percentage of patients who had unconfirmed CR or PR.

'The duration of overall response is measured from the time measurement criteria are first met for CR/PR (whichever is first recorded) until the first date that recurrent or progressive disease is objectively documented (taking as reference for progressive disease the smallest measurements recorded on study). ' [1].

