Duration of Response (weeks) = (Date of PD – Date of first CR/PR [whichever is first recorded] + 1) / 7

- Time to Progression (TTP)

Time to documented PD (based on radiological assessments) will be derived and expressed in the unit of weeks. TTP is defined as the time from first dose of study drug until objective tumor progression; TTP does not include deaths [3]. Based on this definition, PDs will be counted as outcome; patients with last tumor assessment showing CR or PR or SD will be censored at the time of last available tumor assessment per RECIST v1.1; patients who died for any cause (including deaths of disease but with no documented PD) will as well be censored at the time of last available tumor assessment per RECIST v1.1.

TTP (weeks) = (Date of PD – Date of first IMP infusion + 1) / 7

In this study, there is no planned survival status after discontinuation of study treatment, therefore, progression-free survival is not calculated.

PAREXEL International
Statistical Analysis Plan Template for Early Phase Studies

Symphogen A/S
Sym013-01

- Disease control rate (DCR), based on determination of confirmed BOR per RECIST v1.1.

The DCR is defined as the percentage of patients who had confirmed BOR of CR, PR or SD of at least 16 weeks. Definition of duration of TTP corresponds to SD duration; thus, these times will be used to determine if a patient was in SD for at least 16 weeks.

- Changes in sum of diameters of target lesions from baseline to end of trial participation

For patients with measurable disease (i.e., with target lesions), absolute and percent changes in the sum of diameters of target lesions from baseline to end of trial participation will be calculated, the best change will be identified as largest reduction or smallest increase.

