4.2 General Presentation Considerations

Baseline

‘Baseline’ is defined as the last available pre-treatment assessment, considering both scheduled and unscheduled assessments.

Safety assessments at Cycle 1 Day 1 with no time of assessment (i.e. Vital Signs and Body Measurements, ECOG PS, Physical Examination) are assumed to be taken pre-treatment.

End of Treatment (EOT)

‘End of Treatment’ is defined as the first assessment on or after the last dose of study treatment, considering both scheduled and unscheduled assessments.

Unscheduled assessments

Unscheduled assessments will be presented in listings in chronological order.

Post Baseline unscheduled assessments (for Clinical Laboratory, ECG QTc, etc.) will be used for determination of worst result (i.e. Maximum and Minimum post Baseline result) as well as the maximal laboratory CTCAE grade if applicable; also, all post baseline tumor evaluation assessments will be used to derive BOR.

Except considered as Baseline, EOT or worst result, unscheduled assessments will not be included in summaries.

PAREXEL International
Statistical Analysis Plan Template for Early Phase Studies

Symphogen A/S
Sym013-01

Treatment Day

‘Treatment Day’ will be calculated relative to the date of C1/D1 as follow:

- assessments taken before the first infusion of IMP

Treatment Day = Assessment Date - First IMP infusion Date

- assessments after the first infusion of IMP

Treatment Day = Assessment Date - First IMP infusion Date + 1.

Missing Data

In case of partially missing date of birth or date of diagnosis, the following rule will be applied: if year and months are known but day is missing, then the day will be imputed as 15th; in case of only year known, the day and month will be imputed as 15th June.

Specific rules for handling for missing efficacy assessments are detailed in section 4.10.1.3.

Methods for handling missing concomitant medication and adverse events dates are detailed in sections 4.8 and 3.2.4.2 respectively.

Imputations will be used to derive parameters, in listings original data will be presented as collected.

Data Listing

All original and derived parameters for all consented patients will be listed.

All listings will include scheduled and unscheduled measurements.

Unless specified otherwise, data in listings will be presented by dose regimen (Q1W or Q2W), dose group, patient, and visit (ordered by date and time within patient).

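### The SAP sets no cut-off for tumour assessments at the start of subsequent anti-cancer therapy, so a 1-month follow-up scan taken on another drug can enter the Pan-HER efficacy summaries

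*SAP*

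**What the plan says.** **When other therapy may start.** Protocol 7.5.2 prohibits other anti-cancer treatment from C1/D1, "or as specified in the inclusion/exclusion criteria, until the EOT Visit". Protocol 5.3.4 places EOT no later than 10 days after the stop decision and 1M FUP 30 to 37 days after the last dose. Protocol 8.10 adds: "Assessments at the 1M FUP Visit include disease status and subsequent cancer therapy".

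**Who is scanned after EOT.** SAP 3.2.1.1 schedules a CT/MRI at 1M FUP when PD has not been documented by EOT. The EOT scan itself is due only if the previous one is more than 3 weeks old.

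**Which scans each endpoint uses.**
- BOR in general (SAP 4.2, unscheduled assessments): "all post baseline tumor evaluation assessments will be used to derive BOR".
- Confirmed BOR (SAP 3.2.1.1, citing RECIST): "the best overall response is the best response recorded from the start of the study treatment until the end of treatment".
- Unconfirmed BOR (SAP 3.2.1.1): "the Best response is defined as the best response across all time points".
- OR (SAP 3.2): "Documented OR, defined as documented PR or CR, from baseline to end of trial participation". Change in target lesions has the same window. SAP 3.1 makes the 1M FUP visit the end of participation.
- TTP (SAP 3.2.1.1): "patients with last tumor assessment showing CR or PR or SD will be censored at the time of last available tumor assessment". Death without documented PD is the only other censoring case named.
- DCR (SAP 3.2.1.1): confirmed CR or PR, or SD of at least 16 weeks, with SD duration taken from TTP.

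The one rule that stops response assessment when a new intervention begins is in the Part 2 follow-up text (Protocol 5.3.4 and 8.10). It applies after 1M FUP, and Part 2 did not take place (SAP 4.14).

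**The concern.** A patient may stop Pan-HER without PD for toxicity, by choice, or for a treatment failure short of PD (Protocol 6.3.1). That patient can begin another therapy after EOT and still be scanned at 1M FUP. The documents foresee this: Protocol 7.5.2 sends a patient who needs prohibited treatment to EOT and then to 1M FUP, and subsequent therapy is recorded at that visit.

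If the scan counts, shrinkage or stability on the next drug can be reported as Pan-HER activity. Part 1 has no control arm against which such a case would show. The affected outputs are all kept for the abbreviated CSR (SAP 6): the BOR/OR/DCR and TTP tables, the waterfall plots, the Kaplan-Meier curve and the swimmer plot.

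**Working it through.** The plan gives no figure that depends on this rule, so there is none to reproduce. The check has four parts.

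**1. Can new therapy precede the 1M FUP scan?** Assume the stop decision comes 0, 7 or 14 days after the last dose, with EOT 0 to 10 days later. The gap from EOT to 1M FUP runs from 30 − (decision + 10) to 37 − decision:
- decision at day 0: 20 to 37 days
- decision at day 7: 13 to 30 days
- decision at day 14: 6 to 23 days

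The gap is positive in every case. The top of the range needs a decision, and an EOT visit, on the day of the last dose.

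**2. Which endpoints take the scan?**
- *Unconfirmed BOR and OR, best change:* directly, since their windows run over all time points or to the end of participation.
- *TTP:* directly, as an event date or as the last available assessment.
- *Confirmed BOR, confirmed OR and the BOR part of DCR:* unresolved. SAP 4.2 admits all post-baseline scans, while the RECIST sentence in 3.2.1.1 stops at end of treatment. SAP 4.2 also defines End of Treatment as the first assessment on or after the last dose. If the EOT scan was skipped because one was taken within 3 weeks, and that one preceded the last dose, the 1M FUP scan is the first tumour assessment after it. The RECIST sentence therefore does not clearly exclude the scan.
- *Confirmation:* this needs at least 28 days. A PR first seen at 1M FUP has no later Part 1 scan, so it can count only as unconfirmed. The 1M FUP scan can confirm a PR seen at least 28 days before. For a PR first seen at EOT, that requires a gap of 28 days or more, which part 1 allows for decisions at day 0 or 7 but not at day 14.

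**3. The 16-week SD rule.** With duration = (days from first infusion + 1)/7, 16.0 weeks is day 111. A 1M FUP scan reaches it when the last dose was on day 111 − 37 = 74 or later (37-day visit), or on day 111 − 30 = 81 or later (30-day visit). Take a last dose on day 84, a planned dosing day in both schedules:
- end-of-Cycle-2 scan, days 49 to 56: 50/7 = 7.1 to 57/7 = 8.1 weeks
- EOT scan, days 84 to 84 + 24 = 108 (due, since at least 84 − 56 = 28 days have passed): 85/7 = 12.1 to 109/7 = 15.6 weeks
- 1M FUP scan, days 114 to 121: 115/7 = 16.4 to 122/7 = 17.4 weeks

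With SD throughout, the EOT scan leaves this patient below 16 weeks and the 1M FUP scan alone brings the patient into DCR. SD as confirmed BOR is already met at EOT (6-week minimum), so this route does not depend on the conflict in part 2.

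**4. Effect of one patient (exact Clopper-Pearson, all patients in the group evaluable).** For 0 of n, the upper limit is 1 − 0.025^(1/n). For 1 of n, the limits are beta quantiles.
- n = 3: 0% (0 to 70.8) becomes 33.3% (0.8 to 90.6)
- n = 7: 0% (0 to 41.0) becomes 14.3% (0.4 to 57.9)

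Protocol 3.2.4.1 reports cohorts of these sizes: 3 patients at 6 mg/kg Q2W and 7 at 9 mg/kg Q2W.

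**The case against.** The clause in SAP 4.2 deals with unscheduled scans and was not written with later therapy in mind. The section that derives confirmed BOR carries the narrower RECIST window. A reader might infer that BOR, OR and DCR all settle on using every post-baseline scan. The documents do not support that: for confirmed BOR and what follows from it, they conflict. A reader might also infer that any first PR at 1M FUP becomes a confirmed Pan-HER response. The 28-day rule prevents that.

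Exposure is limited. Only patients without PD by EOT have this scan, and 4 to 5 weeks on a new drug beforehand is an extreme case. In the DCR example the patient has had 12 weeks of Pan-HER and a further check at EOT. Crossing 16 weeks does not show that the new drug produced the stability.

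There are partial safeguards. The sponsor and the CRO review BOR patient by patient (SAP 3.2.1.1), and medications and responses by visit are listed. A misattributed case would be visible, but the review has no stated criterion for it.

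For TTP, censoring at a switch is partly a choice of estimand. It may be informative, and it would discard PD seen at 1M FUP that now counts as an event. The present rule therefore does not err only in Pan-HER's favour. This objection stands, and the fix allows for it.

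Finally, all analyses are descriptive (SAP 4.10.1.2), and antitumour effect is the last of six secondary objectives. No error rate, power or Part 2 decision is at stake.

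**Conclusion.** The point holds in limited form. No cut-off at new therapy exists for Part 1. Unconfirmed BOR/OR, best change, TTP and the SD duration used for DCR are directly exposed, and a PR seen earlier can be confirmed by a scan on another drug. For confirmed BOR, confirmed OR and the BOR part of DCR, the SAP gives two windows that must be reconciled.

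The size rests on an assumption: one affected patient moves a 3-patient group by 33.3 points. The documents do not say how many patients switched before 1M FUP, and the number is probably small. A reader might spread the effect over 34 patients, but that is the planned Part 1 number (Protocol 10.1). Enrolment stopped during Part 1 and several dose levels enrolled nobody (SAP 1 and 3.1), so 34 is not an established denominator. The gap calculation also assumes when the stop decision falls.

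The consequence is modest, but the correction is cheap enough to make.

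**What to change.** In SAP 3.2.1.1 and 4.2, state one assessment window for BOR, confirmed and unconfirmed OR, DCR (including SD duration), best change and the waterfall plots: all scheduled and unscheduled post-baseline scans up to the start of any subsequent anti-cancer therapy. Reconcile the RECIST end-of-treatment sentence with the 4.2 clause. Keep the 4.2 wording that admits unscheduled scans, because the same section otherwise leaves unscheduled assessments out of summaries and scans for suspected PD would become ambiguous. Flag later scans in the listings.

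For TTP, censor at the last assessment before new therapy and report the current rule as a sensitivity analysis.

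The cost is SAP wording and one date condition. Subsequent therapy is already collected at 1M FUP (Protocol 8.10), and Protocol 8.2.1 records start dates for medications up to that visit. The downside is that a few scans leave the summaries, and response or disease-control figures may be slightly lower. Patient care does not change.
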